 **To do next week:**

I will:

Keep track of my weight, eating and activity.

**Try my two action plans for
making social cues work for me.**

Answer these questions:

Did my action plans work? _____

If not, what went wrong? _____

What could I do differently next time? _____

Patients will go through the following worksheet during week 6 of radiation/week 8 of diet.

You Can Manage Stress.

Stress is tension or pressure.
Many people react to stress by overeating or being inactive.

What kinds of things make you feel stressed?

What is it like for you when you get stressed?

Ways to prevent stress:

Practice saying, "No."

Try to say "Yes" only when it is important to you.

Share some of your work with others.

Set goals you can reach.

Take charge of your time.

- ❖ Make schedules with the real world in mind.
- ❖ Get organized.

Use problem solving:

- ❖ Describe the problem in detail.
- ❖ Brainstorm your options.
- ❖ Pick one option to try.
- ❖ Make an action plan.
- ❖ Try it. See how it goes.

Plan ahead.

- ❖ Think about the kind of situations that are stressful for you.
- ❖ Plan for how to handle them or work around them.

Keep things in perspective.

- Remember your purpose.**
- ❖ Think of all the good things in your life.

Reach out to people.

Be physically active.

When you can't avoid stress:

Catch yourself feeling stressed as early as you can.
Take a 10-minute "time out."

- ❖ Move those muscles.
- ❖ Pamper yourself. Just take 10 minutes for YOURSELF.
- ❖ Breathe. Try this: Take a full, deep breath. Count to five. Then let go of your breath slowly. Let the muscles in your face, arms, legs, and body go completely loose.

The DPP may cause stress.

Possible source of stress	Way(s) to manage stress	Examples
Extra time spent in food preparation, shopping.	
 - Share some of your work. - Take charge of your time. 	
 - Ask spouse to help shop. - Make double recipes. Freeze part for later.
Feel deprived when can't eat favorite foods.	
 - Set goals you can reach. - Keep things in perspective. 	
 - Allow yourself to have favorite foods in small amounts now and then. - Remind yourself how important preventing diabetes is to you.
Upset if your family doesn't like low-fat foods.	
 - Reach out to people. - Use the steps for solving problems. 	
 - Ask your family to support your efforts to try new foods. - Discuss your feelings and your commitment to weight loss with your family. Brainstorm options with them. Try one.
Feel uncomfortable participating in social activities where high-fat foods are available.	
 - Practice saying, "No." - Reach out to people. - Plan ahead. 	
 - Turn down invitations that aren't important to you. - Call the host or hostess ahead and ask what will be served and if you can bring a low-fat dish. - Before you go to a party, plan what foods you will choose.
Feel stressed by trying to fit activity into an already busy schedule.	
 - Plan ahead. - Problem solve. 	
 - Make an appointment to be active. - Combine activity with other events you plan to do anyhow. (Take a walking meeting. Go hiking with the family.)

WPCORR11STRESS.PT, 10/7/98

Lifestyle Balance
You Can Manage Stress, Page 2

Other major sources of stress for you:

Choose one source of stress. Make a positive action plan:

I will: _____

When? _____

I will do this first: _____

Roadblocks that might come up: I will handle them by:

I will do this to make my success more likely:

How can we help you?

 **To do next week:**

I will:

Keep track of my weight, eating and activity.

Try my action plan for managing stress.

Did it work? If not, what went wrong?

Prior to the final week of their diet, patients will go through this worksheet on staying motivated.

Ways to Stay Motivated.

Changes you've made to be more active:

[figure not shown]

Changes you've made to eat less fat (and fewer calories):

Have you reached your weight goal? Yes No

Have you reached your activity goal? Yes No

If not, what will you do to improve your progress?

SPIC00188MOTIVPT, 10/198

Lifestyle Balance
Ways to Stay Motivated, Page 1

Ways to stay motivated:

1. Stay aware of the benefits you've achieved and hope to achieve.

What did you hope to achieve when you first joined _____ ?
Have you reached these goals?

What would you like to achieve in the next six months _____ ?

2. Recognize your successes.

What changes in your eating and activity do you feel proudest of?

3. Keep visible signs of your progress.

Post weight and activity graphs on your refrigerator door.

Mark your activity milestones on a map toward a particular goal.

Measure yourself (waist, belt size) once a month.

4. Keep track of your weight, eating and activity.

Record your activity daily.

Record what you eat this often: _____

Record your weight on: _____

5. Add variety to your routine.

How have you varied your activity?

What meals, snacks, or foods are you most bored with?

Can you think of some ways to vary this part of your eating?

**6. Set new goals for yourself.
Develop ways to reward yourself when you meet each goal.**

Goals: Specific, short-term, just enough of a challenge.

Rewards: Something you will do or buy **if and only if** you reach your goal.

What are some non-food ways you can reward yourself for reaching a goal?

7. Create some friendly competition.

Set up the kind of competition in which you both win.

[figure not shown]
8. Use the Lifestyle Balance staff and others to help you stay motivated.

Call a Lifestyle Balance staff member, participant, or friend for encouragement and support.

Choose one way to stay motivated that would be helpful to you now.

Make a positive action plan:

Problems
can be solved.

I will: _____

When? _____

I will do this first: _____

Roadblocks that might come up: _____ I will handle them by: _____

I will do this to make my success more likely:

How can we help you?

 **To do next week:**

I will:

Keep track of my weight, eating and activity.

Try my action plan for staying motivated.

Did it work? If not, what went wrong?

Appendix VI. Blood/Tissue Specimen Collection and Banking

Blood

1. Blood specimen collections will be performed on each patient.
2. Timing: baseline at radiation simulation visit, conclusion of diet and 4 weeks after radiation.
3. Collection: Each time, 20-30 cc blood will be collected using two sodium heparin vacutainer tubes.
4. Sample preparation: Blood specimens collected from Thomas Jefferson University should be processed locally the same day of collection. Processed samples (serum and plasma) should be given to [name] or member of her laboratory.
5. Process: All blood specimens collected will be processed locally within 24 hr of collection. The blood specimens will be processed for plasma and serum.
6. Storage: Plasma specimens and serum will be stored in liquid nitrogen or a -70-80°C freezer

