3.3 Secondary Study Endpoints

Investigate measurable changes of patient characteristics and tissue and serum from fasting/CR conditions to determine a metric for evaluating this treatment in future studies.

- Weight: Weight will be monitored as a percent change and by body mass index as weight in kg divided by height in meters squared, at baseline, week 1, 3, 5 and 7, conclusion and 4 weeks after diet is complete.
- Body Fat Measurement: Body fat percentage will be done at baseline, conclusion and 4 weeks after diet is complete and will be determined by the Durnin-Womersley 4-fold technique. All skinfold measurements should be made on the right side of the body in mm using a body fat caliper. Body fat caliper will be placed 1 cm away from thumb and finger, perpendicular to the skinfold, and halfway between the crest and base of fold. A pinch will be maintained with the body fat caliper for 1 to 2 seconds before reading the caliper. Duplicate measurements will be taken at each site, allowing time for skin to regain normal texture and thickness. Measurements will be taken at the:
 - Biceps: Measured on a vertical fold at the upper arms frontside, half way between shoulder and elbow.
 - Triceps: Measured on a vertical fold at mid of the upper arms backside.
 - Scapula: Measured on a diagonal fold on the back, at the lower edge of the scapula. Angle of inclination should be 45°, clockwise.
 - Hip: Measured on a diagonal fold straight over the pelvis, close to the navel. Angle of inclination should be 30°, clockwise.
- Bioimpedance: Bioimpedance will be taken at baseline, conclusion and 4 weeks after diet is completed and will be measured in Ω/m^2 .
- Vitals: Vital signs including temperature, blood pressure, heart rate and respiratory rate will be monitored weekly.
- Serum (collection procedures detailed in Appendix VI):
 - At initiation of diet, conclusion of diet and 4 weeks after diet is complete, fasting labs will be drawn:
 - Clinical Lab: CBC, basic metabolic panel, hemoglobin A1C, triglycerides, insulin, IGF-1, erythrocyte sedimentation rate (ESR), adiponectin, leptin and estradiol
 - Other Serum Markers: IGF-1R, IRS-1, genomic and/or proteomic analysis
 - At week 5: a fasting insulin level will be evaluated.

- **Psycho-social evaluation:** Patients will have psycho-social evaluation using the FACT-B test and the PROMIS cancer fatigue short form at baseline, week 5, conclusion and 4 weeks after conclusion. (Forms detailed in CRFs in Appendix VII)

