6.2.4 Phase III—Post Radiation Treatment

Visit 10: Week 9 of diet, for scheduling purposes. Weight and vital signs will be measured. Patients will be monitored for acute radiation toxicity including skin changes and desquamation. Patients will turn in their food diary from the previous week and dietary counselors will review these with the patients to determine how they can continue to comply with dietary modification. A 24hr recall of diet will be asked of the patient and compared with the diet journal to determine the self-reporting accuracy. Patients will be counseled on behavioral modification for the final week of their diet (see Appendix V for worksheet). Weight and vital signs will be measured.

Visit 11: Week 10 of diet, +/- 3-5 days for scheduling purposes, last day of diet; Fasting blood draw to be done for CBC, basic metabolic panel, hemoglobin A1C, triglycerides, insulin, IGF-1, erythrocyte sedimentation rate (ESR), adiponectin, leptin and estradiol. Separately, blood will be analyzed for IRS-1, IGF-1R. Weight and vital signs will be measured. Conclusion bioimpedance and caliper measurements will be taken. Patients will be monitored for acute radiation toxicity including skin changes and desquamation. Patients will turn in their food diary from the previous week and dietary counselors will review these with the patients to determine how they can continue to comply with dietary modification. A 24hr recall of diet will be asked of the patient and compared with the diet journal to determine self-reporting accuracy. Patients will complete the FACT-B psychosocial evaluation as well as the PROMIS cancer fatigue short form.

Visit 12: 4 weeks after completion of diet. Fasting blood draw to be done for CBC, basic metabolic panel, hemoglobin A1C, triglycerides, insulin, IGF-1, erythrocyte sedimentation rate (ESR), adiponectin, leptin and estradiol. Separately, blood will be analyzed for IRS-1, IGF-1R. Weight, bioimpedance, caliper measurements and vital signs will be measured. Patients will be monitored for acute radiation toxicity including skin changes and desquamation. Patients will turn in their food diary from the last diet week. FACT-B and PROMIS cancer fatigue short form will be administered.

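### Appendix VI names only sodium heparin tubes for the research blood, yet requires serum as well as plasma from it

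*Combined protocol and SAP*

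**What the plan says.** Appendix VI sets out the research blood collection as a numbered list. Draws take place at three time points. At each, "20-30 cc blood will be collected using two sodium heparin vacutainer tubes". The later items ask for two fractions:

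- preparation: "The blood specimens will be processed for plasma and serum";
- transfer to the research laboratory: "Processed samples (serum and plasma) should be given to" the named recipient or her laboratory;
- storage: "Plasma specimens and serum will be stored in liquid nitrogen" or a freezer.

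Section 3.3 makes this appendix the operative procedure for the serum item of the secondary endpoint: "Serum (collection procedures detailed in Appendix VI". Under that item it lists a clinical panel, "Clinical Lab: CBC, basic metabolic panel, hemoglobin A1C, triglycerides, insulin, IGF-1, erythrocyte sedimentation rate (ESR), adiponectin, leptin and estradiol", and then, on its own line, "Other Serum Markers: IGF-1R, IRS-1, genomic and/or proteomic analysis". Section 14 also refers the reader to Appendix VI for the banking details.

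**The concern.** Serum is the fluid that remains after blood has clotted, and heparin stops blood from clotting. A heparin tube therefore gives plasma. The appendix names a container that can deliver one of the two fractions it asks for and not the other. This uses only the ordinary meaning of the words.

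Specific Aim 2 in section 1.2 looks to serum markers for a metric to evaluate the diet in later studies, and section 7.2 models them over time. With one arm, the inference rests on change within patients, so the sample type should be stated and held constant. As written, staff who look for the serum procedure are sent to instructions that produce none. The markers would then be run on a sample type that the protocol does not describe. The fraction obtained is decided by the tube at the draw, and the end-of-diet sample cannot be taken again.

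**Working it through.** The plan gives no figure on this point to reproduce, and no power or error-rate formula applies. The check is a comparison of passages, followed by a count.

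**1. Container against product**

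| Step in Appendix VI | What is specified | Obtainable from heparin tubes? |
|---|---|---|
| Collection | two sodium heparin tubes, 20-30 cc | – |
| Transfer to laboratory | serum and plasma | plasma only |
| Processing | plasma and serum | plasma only |
| Storage | plasma and serum | plasma only |

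Serum is required three times, so it is not a stray word. No other section, including sections 3.3, 6.2, 6.3 and 14 and the visit checklists in Appendix VII, names a tube without anticoagulant or any other tube type.

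**2. Which markers depend on these tubes**

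- Section 6.2.4 describes the clinical laboratory tests first and then adds "Separately, blood will be analyzed for IRS-1, IGF-1R". Section 6.2.2 makes the same separation at baseline and adds genomic or proteomic work.
- The flowchart in section 6.3 has one row for the clinical and hormone tests and another for IGF-1R and IRS-1.
- The simulation and follow-up checklists in Appendix VII have one line for the laboratory tests and another for the blood sent to the research laboratory.

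The affected set is therefore IGF-1R, IRS-1 and any proteomic work. The documents do not say what sample the genomic work would use. Insulin, IGF-1, adiponectin, leptin, estradiol and triglycerides appear to follow the clinical laboratory route. One point cuts the other way: the pointer to Appendix VI in section 3.3 stands on the whole serum item, so the text does not settle this beyond doubt.

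**3. Number of draws**

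Inputs: 3 time points (Appendix VI) and 90 patients (Study Summary; section 7.1).

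Draws = time points × patients = 3 × 90 = 270.

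This is an upper bound. It assumes that all 90 patients enrol and attend every draw, while section 4.5.1 lists many routes to withdrawal. It counts draws that would give no serum, not measurements lost, because each would still give plasma.

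**4. Volume if one tube is changed**

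With equal filling, each tube holds 20/2 = 10 to 30/2 = 15 cc. Switching one of the two leaves 1/2 of the anticoagulated blood, hence about half the banked plasma, with no change in the total drawn.

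**The case against.** The strongest reply is that the collection step simply omits a serum tube. The appendix never says that heparin tubes are the only ones used, and it asks for serum three times, so an omission is at least as likely as a plan without serum. That may well be the cause. It does not remove the point, since Appendix VI is the instruction to which the protocol sends its staff.

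Second, the protocol uses the word serum loosely. Its serum item includes the blood count, hemoglobin A1C and ESR, which are not serum tests, and section 6.2 speaks only of blood being analysed for IGF-1R and IRS-1. No assay is named, and nothing says that plasma would be unsuitable. This stands: the documents do not show that the markers would be unmeasurable.

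Third, a reader might infer that sample type would drift between visits and be mixed with the effect of the diet. The documents do not support that. Followed exactly, the appendix gives heparin plasma at every visit, and the models in section 7.2 would compare like with like. A shift would arise only if staff departed from the appendix differently at different visits, and no passage suggests that they would.

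**Conclusion.** The inconsistency is real and lies within one appendix: the tubes named cannot give one of the two fractions required. Followed as written, up to 270 research draws would yield heparin plasma and no serum for IGF-1R, IRS-1 and any proteomic work. This rests on the absence of any other tube type in the documents, and the count rests on full enrolment and attendance.

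A reader might go further and conclude that the serum part of the secondary objective as a whole would be lost. The documents do not support this. The clinical panel is listed, scheduled and checked off apart from the research blood and is probably unaffected, and plasma for the research markers would still exist.

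Neither primary endpoint (adherence, skin toxicity), nor the sample size, nor any decision rule depends on the point. It is a minor operational correction to a secondary endpoint.

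**What to change.** In Appendix VI, state the tube type and volume for each fraction. Two routes are open:

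- **Keep serum.** For example, specify one of the two tubes without anticoagulant, within the same 20-30 cc and the same venepuncture. The cost is a different tube and about half as much banked plasma.
- **Use plasma.** Drop serum from Appendix VI and restate the research markers as plasma wherever they are called serum: the Study Summary and sections 1.1, 1.2, 2.2, 3.3 and 7.2. The cost is wording only, but every place must be changed or a new contradiction appears. The research laboratory should first confirm that its assays accept heparin plasma, since the documents do not say.

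Under either route, fix one sample type per marker for all three time points. The third time point should be reconciled in the same edit: Appendix VI counts four weeks from radiation, whereas sections 2.2, 3.3 and 6.2.4 count from the end of the diet. Neither route adds a visit, a needle stick or blood volume.

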Appendix VII. Case Report Forms

THOMAS JEFFERSON UNIVERSITY HOSPITAL DEPARTMENT OF RADIATION ONCOLOGY

CAREFOR Study: A Feasibility Pilot Trial Evaluating Caloric Restriction for Oncology Research
in Early Stage Breast Cancer Patients

REGISTRATION FORM

Patient's Initials_____ Case#_____ Dose Level_____

MR#_____ Date of birth_____

Address_____

Telephone_____

Sex_____ Race_____ Ethnicity_____

Insurance_____

Radiation Oncologist:_____

Medical Oncologist:_____

Resident:_____

Signature_____ Date_____

CAREFOR Study Case Report Form (CRF)—Screening Visit

Date of Screening: _____

Patient Demographics

Age: _____ Race: _____

Current Address (for mailing purposes):

Emergency Contact: _____

Marital Status: _____

Highest Education Level Completed: _____

Past Medical History and Relevant Clinical Information

Date of Diagnosis: _____

How was the mass found?

- MMG
- SBE
- Physician Exam
- Other: _____

Date of most recent mammogram: _____

Side of Breast Mass (L v. R): _____

Previous History of Breast Cancer: _____

Family History of Breast Cancer: _____

If applicable, what treatment was received for previous breast cancer: _____

_____ Previous History of any
other malignancy (include dates of diagnosis and NED date): _____

Is this patient a candidate for breast conservation? _____
_____ Oral

Contraceptive Use (current or past): Y or N

Hormone Replacement Use: Y or N

Date of last period _____ Age at menarche: _____

Gravida/Para: _____

Previous diagnosis of any of the following:

- Unstable Angina
- Coronary Artery Disease

Myocardial Infarct, if yes please indicate date of event: _____

CHF

Valvular Disease

Arrhythmias/Pacemaker Placement

Diabetes

Severe Asthma

Autoimmune Disorder (specifically SLE, scleroderma, dermatomyositis)

Any Disease Requiring Chronic Steroid Use

Inflammatory Bowel Disease

Celiac Disease

Chronic Pancreatitis

Chronic Diarrhea or Vomiting

Active Eating Disorder

Renal Failure or CKD

Pituitary Secreting Tumor

HIV Positive Status or AIDS including any AIDS defining illness

Hepatic Insufficiency

Recent hospitalization (within the last 6 months, include diagnosis and length of stay): _____

Recent Weight Loss (include baseline weight and pounds lost): _____

Surgical History

Please indicate any major surgeries, the date or at least the year of the surgery and whether or not there were any post-op complications:

Surgery Date

Pre-op Diagnosis

Post-Op Complications

Pertinent Social History

Current Occupation: _____

Habitation Status (alone or with family): _____

Alcohol Use: _____

Previous or Current Use of Illicit Drugs: _____

Smoker (indicate pack/year for current or past and year of cessation): _____

Currently Sexually Active: Y or N

If yes, what type of contraception is being used? _____

If no contraception, is the patient willing to use contraception for the duration of the study/treatment period? _____

Allergies:

Current Medications (indicate dose, route, frequency and start date):

Medication	Dose	Route	Frequency	Start Date
_____	_____	_____	_____	_____
_____	_____	_____	_____	_____
_____	_____	_____	_____	_____
_____	_____	_____	_____	_____
_____	_____	_____	_____	_____
_____	_____	_____	_____	_____
_____	_____	_____	_____	_____
_____	_____	_____	_____	_____

Physical Examination

Height: _____

Weight: _____

BMI: _____

Karnofsky Performance Status:

Please assess the patient's performance status based on the table provided. Circle the most appropriate functional capacity.

Able to carry on normal activity and to work; no special care needed.	100	Normal no complaints; no evidence of disease.
	90	Able to carry on normal activity; minor signs or symptoms of disease.
	80	Normal activity with effort; some signs or symptoms of disease.
Unable to work; able to live at home and care for most personal needs; varying amount of assistance needed.	70	Cares for self; unable to carry on normal activity or to do active work.
	60	Requires occasional assistance, but is able to care for most of his personal needs.
	50	Requires considerable assistance and frequent medical care.
Unable to care for self; requires equivalent of institutional or hospital care; disease may be progressing rapidly.	40	Disabled; requires special care and assistance.
	30	Severely disabled; hospital admission is indicated although death not imminent.
	20	Very sick; hospital admission necessary; active supportive treatment necessary.
	10	Moribund; fatal processes progressing rapidly.
	0	Dead

We will work together as a TEAM.

I will count on you to:

- ❖ Come to sessions and bring your Lifestyle Balance notebook.
Call 24 hours ahead if you must miss a session.
- ❖ Do your best to reach your eating and activity goals.
That includes doing home activities to practice what you learn.
- ❖ Keep track of your eating and activity 7 days a week.
Be honest. (Don't try to "please me.")
- ❖ Keep track of your weight at home.
- ❖ Let me know if you have any problems.
- ❖ Stay willing and open to change. Always "hang in there."

You can count on me to:

- ❖ Go over your records of what you eat and your activity.
Notice what you are doing well and what can be improved.
- ❖ Answer your questions.
- ❖ Be honest.
- ❖ Stand by you during hard times.
- ❖ Believe you can reach your eating and activity goals.
Always "hang in there" for you. Support and help you.

We agree to work together in the ways described above.

Signed: _____

**Thomas Jefferson University
Kimmel Cancer Center**

CAREFOR Inclusion/Exclusion Criteria Checklist

Inclusion Criteria:

Patients must meet all of the following criteria in order to be considered for entry into the CAREFOR trial.

- Pathologically confirmed diagnosis of DCIS or invasive breast cancer
- Female patient, 18 years or older
- Candidate for breast conservation
- Karnofsky performance status at least 80%
- Negative serum beta-hCG if appropriate
- Willing to use contraception, not sexually active or post-menopausal
- BMI > 21
- Weight > 100lbs

Exclusion Criteria:

In addition to meeting inclusion criteria, patients are ineligible for enrollment if any of the following exclusion criteria are met.

- Intentional weight loss > 10% of total body weight within the last 3 months prior to trial enrollment.
- Prior non-breast invasive malignancy, unless free of disease for at least 1 year prior to trial enrollment.
- Two or more breast cancers not resectable through a single lumpectomy site.
- Non-epithelial breast malignancies such as sarcoma or lymphoma.
- Prior radiotherapy to ipsilateral breast that would result in overlapping radiation fields.
- Severe, active comorbidities to include any one of the following:
 - Unstable angina or CHF requiring hospitalization in the last 6 months
 - COPD exacerbation requiring hospitalization within 30 days of registration
 - Transmural myocardial infarct in the past 6 months
 - Acute bacterial or fungal infection requiring IV antibiotics at the time of registration

- Hepatic insufficiency resulting in clinical jaundice
- AIDS or HIV positive according to CDC guidelines
- Active systemic lupus erythematosus, scleroderma or dermatomyositis with rash.
- Medical or psychiatric condition preventing the patient from providing informed consent or from adhering to diet guidelines.
- Currently taking diet supplements
- Active gastrointestinal/malabsorption syndrome to include:
 - Inflammatory Bowel Disease
 - Celiac Disease
 - Chronic Pancreatitis
 - Chronic Diarrhea or Vomiting
 - Active Eating Disorder
- Currently using steroids
-
- Active/history of substance abuse or dependency to include prescription or illicit drugs as well as alcohol.
- Decisionally impaired patients.

Checklist for Screening Visit:

Informed Consent for Trial Obtained	
All Sections of CRF Completed	
Inclusion/Exclusion Criteria Evaluated	
Blood draw: Beta-HCG	
H&P; Performance Status	
Weight, BMI	
Based on screening patient appears eligible	

CAREFOR Study Case Report Form (CRF)—Radiation Treatment Planning Visit

Date of Sim Visit: _____

Lumpectomy Details

Please indicate the actual date of the lumpectomy, whether or not there were any post-op complications and the status of the Path report:

Surgery DatePre-op DiagnosisPost-Op Complications_____

Path Report Received? Y or N

Attach a copy of the Path Report to this visit.

Verify Allergies:_____

_____**Changes to Current Medications (indicate dose, route, frequency and start date):**

Medication

Dose

Route

Frequency

Start Date

Physical Examination

Height: _____ Weight: _____ BMI: _____
 Vital Signs: BP: _____ HR: _____ Temp: _____ RR: _____
 Caliper Measurements: _____

Bioimpedance Measurement: _____

Please indicate the status (normal or abnormal) of each system listed below. If abnormal, please make notes. Give detailed description of breast exam in the notes section.

Organ System	Status	Notes
CVS	Normal Abnormal	_____
Pulm	Normal Abnormal	_____ _____
GI	Normal Abnormal	_____ _____
Neuro	Normal Abnormal	_____ _____
Breast	Normal Abnormal	_____ _____ _____

CTCAE v4.0 Evaluation

Please evaluate the patient at baseline for comparison during and post-radiation.

Adverse Event	Grade				
	1	2	3	4	5
Dermatitis radiation	Faint erythema or dry desquamation	Moderate to brisk erythema; patchy moist desquamation, mostly confined to skin folds and creases; moderate edema	Moist desquamation in areas other than skin folds and creases; bleeding induced by minor trauma or abrasion	Life-threatening consequences; skin necrosis or ulceration of full thickness dermis; spontaneous bleeding from involved site; skin graft indicated	Death
Definition: A finding of cutaneous inflammatory reaction occurring as a result of exposure to biologically effective levels of ionizing radiation.					
Skin hyperpigmentation	Hyperpigmentation covering <10% BSA; no psychosocial impact	Hyperpigmentation covering >10% BSA; associated psychosocial impact	-	-	-
Definition: A disorder characterized by darkening of the skin due to excessive melanin deposition.					
Fatigue	Fatigue relieved by rest	Fatigue not relieved by rest; limiting instrumental ADL	Fatigue not relieved by rest, limiting self care ADL	-	-
Definition: A disorder characterized by a state of generalized weakness with a pronounced inability to summon sufficient energy to accomplish daily activities.					

FACT-B (Version 4)

Below is a list of statements that other people with your illness have said are important. Please circle or mark one number per line to indicate your response as it applies to the past 7 days.

PHYSICAL WELL-BEING		Not at all	A little bit	Some- what	Quite a bit	Very much
GP1	I have a lack of energy	0	1	2	3	4
GP2	I have nausea	0	1	2	3	4
GP3	Because of my physical condition, I have trouble meeting the needs of my family	0	1	2	3	4
GP4	I have pain	0	1	2	3	4
GP5	I am bothered by side effects of treatment	0	1	2	3	4
GP6	I feel ill	0	1	2	3	4
GP7	I am forced to spend time in bed	0	1	2	3	4

SOCIAL/FAMILY WELL-BEING		Not at all	A little bit	Some- what	Quite a bit	Very much
GS1	I feel close to my friends	0	1	2	3	4
GS2	I get emotional support from my family	0	1	2	3	4
GS3	I get support from my friends	0	1	2	3	4
GS4	My family has accepted my illness	0	1	2	3	4
GS5	I am satisfied with family communication about my illness	0	1	2	3	4
GS6	I feel close to my partner (or the person who is my main support)	0	1	2	3	4
Q1	Regardless of your current level of sexual activity, please answer the following question. If you prefer not to answer it, please mark this box  and go to the next section.					
GS7	I am satisfied with my sex life	0	1	2	3	4

FACT-B (Version 4)

Please circle or mark one number per line to indicate your response as it applies to the past 7 days.

EMOTIONAL WELL-BEING		Not at all	A little bit	Some- what	Quite a bit	Very much
GE1	I feel sad	0	1	2	3	4
GE2	I am satisfied with how I am coping with my illness.....	0	1	2	3	4
GE3	I am losing hope in the fight against my illness	0	1	2	3	4
GE4	I feel nervous	0	1	2	3	4
GE5	I worry about dying	0	1	2	3	4
GE6	I worry that my condition will get worse	0	1	2	3	4

FUNCTIONAL WELL-BEING		Not at all	A little bit	Some- what	Quite a bit	Very much
GF1	I am able to work (include work at home)	0	1	2	3	4
GF2	My work (include work at home) is fulfilling.....	0	1	2	3	4
GF3	I am able to enjoy life.....	0	1	2	3	4
GF4	I have accepted my illness.....	0	1	2	3	4
GF5	I am sleeping well	0	1	2	3	4
GF6	I am enjoying the things I usually do for fun	0	1	2	3	4
GF7	I am content with the quality of my life right now.....	0	1	2	3	4

FACT-B (Version 4)

Please circle or mark one number per line to indicate your response as it applies to the past 7 days.

ADDITIONAL CONCERNS		Not at all	A little bit	Some- what	Quite a bit	Very much
B1	I have been short of breath.....	0	1	2	3	4
B2	I am self-conscious about the way I dress.....	0	1	2	3	4
B3	One or both of my arms are swollen or tender.....	0	1	2	3	4
B4	I feel sexually attractive	0	1	2	3	4
B5	I am bothered by hair loss	0	1	2	3	4
B6	I worry that other members of my family might someday get the same illness I have	0	1	2	3	4
B7	I worry about the effect of stress on my illness	0	1	2	3	4
B8	I am bothered by a change in weight	0	1	2	3	4
B9	I am able to feel like a woman	0	1	2	3	4
P2	I have certain parts of my body where I experience pain....	0	1	2	3	4

Table 2. Preliminary PROMIS Cancer Fatigue Short Form

Please respond to each question by checking one box

Item	In the Past 7 Days ...	Never	Rarely	Sometimes	Often	Always
FATEXP 20	How often did you feel tired?	 1	 2	 3	 4	 5
FATEXP 5	How often did you experience extreme exhaustion?	 1	 2	 3	 4	 5
FATEXP 18	How often did you run out of energy?	 1	 2	 3	 4	 5
FATIMP 33	How often did your fatigue limit you at work (include work at home)?	 1	 2	 3	 4	 5
FATIMP 30	How often were you too tired to think clearly?	 1	 2	 3	 4	 5
FATIMP 21	How often were you too tired to take a bath or shower?	 1	 2	 3	 4	 5
FATIMP 40	How often did you have enough energy to exercise strenuously?	 1	 2	 3	 4	 5

Abbreviations: PROMIS, Patient-Reported Outcomes Measurement Information System; FATEXP, Fatigue Experience; FATIMP, Fatigue Impact.
Reprinted with permission of the PROMIS Health Organization and the PROMIS Cooperative Group.

Checklist for Sim Visit:

Pathology Report Obtained and Attached	
Baseline Labs: CBC w/diff, CMP, HbA1c Serum: IGF-1, adiponectin, leptin, estradiol, triglycerides, ESR, insulin, glucose	
Blood Sample sent to [name] lab for further analysis	
All Sections of CRF Completed	
FACT-B Completed by patient	
Weight, BMI, Body fat percent, bioimpedance	
Food diaries collected at this visit	
Dietary Counseling for caloric restriction diet alterations	

Please attach a copy of patient's labs when available.
Please attach a copy of food diary.

CAREFOR Study Case Report Form (CRF)—Diet Support Visit: Day 7 of CR Diet

Date of Visit: _____

Changes to Current Medications (indicate dose, route, frequency and start date):

Medication	Dose	Route	Frequency	Start Date
_____	_____	_____	_____	_____
_____	_____	_____	_____	_____
_____	_____	_____	_____	_____

Height: _____ Weight: _____ BMI: _____
 Vital Signs: BP: _____ HR: _____ Temp: _____ RR: _____

Food Diary Received and Completed: Y or N
 If no, must collect at next visit.

CAREFOR Study Case Report Form (CRF)—Diet Support Visit: Day 14 of CR Diet

Date of Visit: _____

Changes to Current Medications (indicate dose, route, frequency and start date):

Medication	Dose	Route	Frequency	Start Date
_____	_____	_____	_____	_____
_____	_____	_____	_____	_____
_____	_____	_____	_____	_____

Height: _____ Weight: _____ BMI: _____
 Vital Signs: BP: _____ HR: _____ Temp: _____ RR: _____

Food Diary Received and Completed: Y or N
 If no, must collect at next visit.

CAREFOR Study Case Report Form (CRF)—Radiation Treatment

Date of Visit: _____ Weeks of Radiation Completed: _____

Changes to Current Medications (indicate dose, route, frequency and start date):

Medication	Dose	Route	Frequency	Start Date

Food Diary Received and Completed: Y or N If no, must collect at next visit.

Physical Examination

Height: _____ Weight: _____ BMI: _____
 Vital Signs: BP: _____ HR: _____ Temp: _____ RR: _____

Please indicate the status (normal or abnormal) of each system listed below. If abnormal, please make notes. Give detailed description of breast exam in the notes section.

Breast	Normal	Abnormal	_____
Erythema	Mild	Moderate	Severe
Hyperpigmentation	Mild	Moderate	Severe
Desquamation	Yes	No	
Dermatitis	Yes	No	
Edema	Yes	No	

CTCAE v4.0 Evaluation

Adverse Event	Grade				
	1	2	3	4	5
Dermatitis radiation	Faint erythema or dry desquamation	Moderate to brisk erythema; patchy moist desquamation, mostly confined to skin folds and creases; moderate edema	Moist desquamation in areas other than skin folds and creases; bleeding induced by minor trauma or abrasion	Life-threatening consequences; skin necrosis or ulceration of full thickness dermis; spontaneous bleeding from involved site; skin graft indicated	Death
Definition: A finding of cutaneous inflammatory reaction occurring as a result of exposure to biologically effective levels of ionizing radiation.					
Skin hyperpigmentation	Hyperpigmentation covering <10% BSA; no psychosocial impact	Hyperpigmentation covering >10% BSA; associated psychosocial impact	-	-	-
Definition: A disorder characterized by darkening of the skin due to excessive melanin deposition.					
Fatigue	Fatigue relieved by rest	Fatigue not relieved by rest; limiting instrumental ADL	Fatigue not relieved by rest, limiting self care ADL	-	-
Definition: A disorder characterized by a state of generalized weakness with a pronounced inability to summon sufficient energy to accomplish daily activities.					

Checklist for Visit:

All Sections of CRF Completed	

FACT-B (Version 4)

Below is a list of statements that other people with your illness have said are important. Please circle or mark one number per line to indicate your response as it applies to the past 7 days.

PHYSICAL WELL-BEING		Not at all	A little bit	Some- what	Quite a bit	Very much
GP1	I have a lack of energy	0	1	2	3	4
GP2	I have nausea	0	1	2	3	4
GP3	Because of my physical condition, I have trouble meeting the needs of my family	0	1	2	3	4
GP4	I have pain	0	1	2	3	4
GP5	I am bothered by side effects of treatment	0	1	2	3	4
GP6	I feel ill	0	1	2	3	4
GP7	I am forced to spend time in bed	0	1	2	3	4

SOCIAL/FAMILY WELL-BEING		Not at all	A little bit	Some- what	Quite a bit	Very much
GS1	I feel close to my friends	0	1	2	3	4
GS2	I get emotional support from my family	0	1	2	3	4
GS3	I get support from my friends	0	1	2	3	4
GS4	My family has accepted my illness	0	1	2	3	4
GS5	I am satisfied with family communication about my illness	0	1	2	3	4
GS6	I feel close to my partner (or the person who is my main support)	0	1	2	3	4
